## 5.6. Subject Disposition

Based on the screened set, a subject data listing will give an overview of the following screening and randomization information (one row for each subject):

- Protocol version under which the subject has signed the initial informed consent
- Date of initial informed consent
- Duration of the screening period
- If screening failure. If so, reasons for screening failure
- Date of randomization, strata used for randomization, a flag if the subject was miss-stratified, treatment assignment, and initial screening number (if re-screened)

A separate listing will just include the subjects with an extended screening period due to the COVID-19 pandemic allowed by the Investigator. The identified subjects will be provided to Cytel after the BDRM.

Sponsor:	TauRx Therapeutics Ltd.		
Protocol:	TRx-237-039		
Document Version No.:	3.0	Document Date:	07-JUN-2023

Subjects who are mis-stratified during the randomization are flagged in the aforementioned listing, but will be also listed separately with the following information: randomized treatment group, strata used for randomization, and correct strata values.

Based on the ITT population, a subject data listing will give an overview of the following disposition information (one row for each subject):

- Protocol version under which the subject has been randomized
- First and last dose dates of study drug intake
- Date of study exit
- A flag for the completion of the study, and a flag for the TOTOS (see Section 4.4)
- All reasons why the subject did not complete the study, and a flag for the primary reason
- For the TOTOS, the reason why the subject discontinued the study drug

Based on the ITT population, a subject by-visit listing, including all planned and unplanned visits, will be created with the following information: randomized treatment group, visit name, and visit date range (including study day). Visit windowing will not be performed for this listing, but visits with a clear wrong label, with a visit date range outside of the associated visit window, will be flagged.

Based on the ITT population, a subject data listing will provide an overview of the double-blind treatment phase populations (see Section 3.1.1) and will list the following events (sorted by subject, and date; one row for each event):

- Affiliation to the study populations (one column per study population)
- Date of initial informed consent
- Date of randomization
- Protocol re-consents, with the protocol version and signing dates (one row for each re-consent)
- Date and primary reason of study discontinuation
- Date of study drug discontinuation, if study drug discontinuation is permanent and if the date is different from the date of study discontinuation
- Discontinuation date of AChEI and/or memantine for purposes of the study (if available)
- Date(s) of COVID-19 infection
- Date(s) of COVID-19 vaccination
- Date of Week 52 visit

Sponsor:	TauRx Therapeutics Ltd.		
Protocol:	TRx-237-039		
Document Version No.:	3.0	Document Date:	07-JUN-2023

---

The number of screening failure reasons will be tabulated (by region, and total). For large study sites, separate tables might be provided.

Information on the number of subjects randomized, the number of subjects in each analysis population, the number of subjects completing the study as well as the double-blind treatment phase (subsets on and off treatment), the number of subjects discontinuing the study drug but continuing the study (TOTOS), the primary reason for discontinuation of study drug and study, and all reasons for discontinuation of study drug and study will be tabulated. This will be done by treatment group and overall, for the ITT, E-MITT, E-MITTv5, ITTv5, and PPv5 populations, separately. Furthermore, based on the ITT population, this will be tabulated by region.

If the reason for discontinuation of study drug is missing the primary reason for discontinuation of study will be used instead.

## 5.7. Demographic and Baseline Characteristics

Data will be provided in subject data listings, based on the ITT population.

Demographic and Baseline characteristics will be summarized for the ITT, E-MITT, E-MITTv5, ITTv5, and PPv5 populations. This will also be done for subgroups (based on the ITTv5 population) by use of AChEI and/or memantine prior to Baseline, for subjects characterized as mild AD or MCI-AD (MMSE: 20-27), for subjects characterized as moderate AD (MMSE: 16-19), by region, and for highly recruiting sites (more than 10% of randomized subjects).

General baseline information to be summarized include age at informed consent, sex, ethnicity (Not Hispanic or Latino, Hispanic or Latino) including only the US sites, race, and geographic region; height, weight, creatinine clearance, smoking history, childbearing status/contraception, age at leaving full-time education, and Fazekas score (periventricular white matter score, deep white matter score, and overall score = maximum of periventricular white matter score and deep white matter score).

Regarding the race: If race was answered in the eCRF with "not reported" or with a similar comment in "other", such as "NA", "NA in France", "not allowed by law", "not applicable", "not authorized", or "not permitted by law", race is set to unknown.

Disease specific Baseline characteristics include the verified AD diagnosis (probable AD dementia, MCI-AD [mild cognitive impairment due to AD], based on the Diagnostic Verification form), time from diagnosis of AD to informed consent (years) and time from presumptive AD diagnosis to informed consent (years), ApoE genotype (in the subset who provide consent), MMSE, CDR, and previous use of an AChEI and/or memantine. Additionally, a summary of the amyloid PET will be provided, whether it was previously done or within this study. The Diagnostic Verification form was not available for subjects who have been randomized under protocol version 2.1, since only subjects with mild AD were included (see Section 1.3), therefore these subjects will be allocated to the probable AD dementia subgroup. The AD diagnosis is defined as medical history of cognitive impairment and is identified by the following

Sponsor:	TauRx Therapeutics Ltd.		
Protocol:	TRx-237-039		
Document Version No.:	3.0	Document Date:	07-JUN-2023

medical history Preferred Terms (PT): Dementia Alzheimer's type, Cognitive disorder, Memory impairment, Transient global amnesia, Amnesia, Amnestic disorder, Dementia, Mixed dementia. The presumptive AD diagnosis is defined as the earliest of the following dates:

- Use of AD medication: ATC code N06DA (e.g., Donepezil, Galantamine, Rivastigmine), and ATC code N06DX (Memantine, and 'other anti-dementia drugs')
- Positive amyloid PET scan
- Verified AD diagnosis

Medical history (coding see Section 4.3) will be summarized in a table presenting the numbers and percentages of subjects with medical history terms in a given MedDRA System Organ Classification (SOC) for the ITT and ITTv5 population.

Analysis of recently used medications and concomitant medications is described in the following Section 5.8.

No formal statistical comparisons of treatment groups for any Baseline characteristics will be performed.

#### **5.8. Prior and Concomitant Medications**

Prior used medications (discontinued before the start of study drug) and concomitant medications (on medication at the first dose of study drug or after) will be coded using the 01 March 2017 version of the WHO drug dictionary and the Anatomical Therapeutic Classification (ATC) level 1 term, ATC level 3 term, and PT. If the end-date and/or start-date are missing, the medication will be allocated to the concomitant medication.

If a medication date or time is missing or partially missing and it cannot be determined whether it was taken prior to or concomitantly with treatment, it will be considered a concomitant medication.

The use of prior medications, and concomitant medications will be included in subject data listings for the ITT population. For subjects who previously used an AChEI and/or memantine, the start and stop date of medication, whether the medication was stopped prior to screening or between screening and randomization, and reason for stopping usage will be listed separately; this listing will include a flag for subjects randomized under the UK study protocol version 5.0 or higher, since for these subjects, AChEI and/or memantine should end before the start of screening. A subset listing will also be provided for subjects who were using an antipsychotic treatment (see Section 10.4), which includes the reasons for use as well.

The following summaries/tabulations will be prepared for the ITT and ITTv5 populations.

Tabulations with frequency and percentage, by treatment group and medication, will be prepared separately for all prior, for all concomitantly used drugs (used at the time of first study drug or after),

Sponsor:	TauRx Therapeutics Ltd.		
Protocol:	TRx-237-039		
Document Version No.:	3.0	Document Date:	07-JUN-2023

---

and for all concomitantly used drugs that the patient is on at the time of first study drug, where subjects reporting more than one medication are counted only once within each level summation.

Summary tables will be provided, showing the numbers of subjects with initiated treatments of: SSRI/SNRI (see Section 12.4), drugs of serotonergic potential (see latest version of the Serotonergic Drugs List – a Sponsor controlled document, which was distributed to Cytel prior to the database lock of the double-blind treatment phase), and any antipsychotic medications. For antipsychotics initiated on-treatment, the reasons for use will be also summarized.

For subjects who previously used an AChEI and/or memantine, the reasons for stopping such medications, duration of use, and duration of time since stopping prior to randomization will be tabulated.

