- At Screening, medications administered within the last 90 days will be recorded, with the exception of anti-dementia medications, where lifetime use (as far as possible) is to be recorded. Changes in concomitant medications and any new concomitant medications will be recorded at all visits, including the telephone contact during the open-label, delayed-start phase, and reviewed by a medical assessor (physician/MD/DO). For antipsychotics, the reason for use should be documented (see Section 13.4).

Further details regarding alternate arrangements for sample collection and shipment that may be implemented due to COVID-19 are described in Section 10.2.

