To calculate descriptive / inferential statistics for laboratory values containing values below/above the limit of quantification, the following general rule of thumb will be applied: each laboratory value below/above the limit of quantification will be imputed numerically to the nearest value below/above the limit, respecting the same number of decimal places than numerical values (e.g., if the number of decimal places=0, subtract/add 1 to the limit of quantification (LOQ); if the number of decimal places=1, subtract/add 0.1 to the LOQ, etc.). Is the LOQ already the lowest value larger than zero, the LOQ will be imputed numerically to the nearest value below the limit with one more decimal place (e.g., if the LOQ is 1, subtract 0.1 from the LOQ: 0.9). The subject data listings will not show the imputed value, but that the value is below or above the limit of quantification.

Partial dates will be reviewed and imputed (where possible) after the BDRM and before unblinding, potentially resulting in an Excel file, which will be provided to Cytel for the use in the analysis. Remaining cases (if existing), which are required for calculation, or cases for which no additional information is provided after the BDRM or if no file has been generated will be handled as follows:

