#### Start dates

- For missing start day only: Day will be imputed as the first day of the month (i.e., 1) with the following exception: if the partial date falls in the same month and year as the first date of dosing, then the partial date will be imputed to equal the first date of dosing (unless the known end date lies before the first date of dosing, when imputing the incomplete start date).
- For missing start day and month: Day and month will be imputed as the first day of the year (i.e., 1 January) with the following exception: if the partial date falls in the same year as the first date of dosing, then the partial date will be imputed to equal the first date of dosing (unless the known end date lies before the first date of dosing, when imputing the incomplete start date).

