- COVID-19 infection, a Pearson's chi-square test is used to compare the frequencies pairwise versus the control group
- *TauRx AE Groupings:* Subsets of TEAEs (defined by PT, the latest version of this allocation list, which is to be used in the analysis, was provided to Cytel prior to the database lock of the double-blind treatment phase), summarized per grouping and sub-grouping (separate columns for true placebo and MTC), repeated for the Safetyv5 population
  - Group: Targeted Gastrointestinal Events
    - Sub-group: Diarrhea
    - Sub-group: Gastrointestinal Irritation
    - Sub-group: Nausea/Vomiting
  - Group: Renal and Urinary Disorders (Including Infections)
    - Sub-group: Urinary Tract Infection
    - Sub-group: Urinary Frequency/Urgency

Sponsor:	TauRx Therapeutics Ltd.		
Protocol:	TRx-237-039		
Document Version No.:	3.0	Document Date:	07-JUN-2023

- Group: Anemia and Related Terms
  - Subgroup: Anemia (excluding vitamin deficiencies)
- Group: Falls and Related Terms
  - Sub-group: Falls
- Group: Hypersensitivity
  - Sub-group: Rash
- Group: Renal Function Impairment
- Group: Hepatic Function Impairment
- Group: Behavioral and Psychological Symptoms of Dementia
  - Sub-group: Affective/Anxiety Symptoms
  - Sub-group: Behavioral Symptoms
  - Sub-group Psychotic Symptoms
  - Sub-group: Sleep Disorders
- Group: Cardiac Ischemia
- TauRx AE Groupings will be repeated for the following subgroups, showing only the main *TauRx AE Groupings*:
  - AChEI/memantine use (prior use, never used) [binary], repeated for
    - Discontinuation of AChEI and/or memantine before entering the study
    - Discontinuation of AChEI and/or memantine for purposes of study participation
  - Age group (<75 years, ≥75 years) [binary]
  - Sex (male, female) [binary]
  - Race (White, non-White) [binary], Race = White (if only race checked), otherwise Race = non-White (even if multiple races, including White, were checked)
  - Renal Function at Baseline: Creatinine Clearance (≤ 50 mL/min, > 50 mL/min) [binary]
  - Use or no use of concomitant medications with serotonergic potential (see latest version of the Serotonergic Drugs List, Section 5.8) at any time during the study [binary]
  - Use or no use of SSRI/SNRI [binary]
  - Use or no use of MAOI [binary]

Sponsor:	TauRx Therapeutics Ltd.		
Protocol:	TRx-237-039		
Document Version No.:	3.0	Document Date:	07-JUN-2023

---

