#### **6.9. Prior and Concomitant Medications**

Any medication that has been discontinued before the intake of the first dose of the open-label treatment phase study drug will be defined as prior medication. Any medication that was taken at the day of the first dose of the open-label treatment phase study drug or after will be defined as concomitant medication. Prior used medications and concomitant medications will be coded using the 01 March 2017 version of the WHO drug dictionary and the ATC level 1 term, ATC level 3 term, and PT will be presented in the analysis.

Data conventions are as described in Section 5.8.

The subject data listing of prior medications, and concomitant medications of the double-blind treatment phase will be updated, and the records of the open-label treatment phase medications will be added. An additional flag will be added to indicate the concomitant medications of the open-label treatment phase. A subset of this subject data listing will also be provided for subjects who were using

Sponsor:	TauRx Therapeutics Ltd.		
Protocol:	TRx-237-039		
Document Version No.:	3.0	Document Date:	07-JUN-2023

an antipsychotic treatment (during the double-blind or open-label treatment phase, see Section 12.4), including the reasons for use.

The following summaries/tabulations will be prepared for the ITTv5-OL and ITT-OL populations.

Tabulations with frequency and percentage, by treatment history and for the pooled treatment histories, will be prepared separately for all prior, for all concomitantly used drugs, and for all concomitantly used drugs that the patient is on at the time of the first dose of the open-label treatment phase study drug. Subjects reporting more than one medication are counted only once within each level summation.

Summary tables will be provided, showing the numbers of subjects with initiated treatments of SSRI/SNRI (see Section 12.4), drugs of serotonergic potential (see latest version of the Serotonergic Drugs List, Section 5.8), and any antipsychotic medications. For antipsychotics initiated on-treatment, the reasons for use will be also summarized.

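### SAP 5.8 gives two inconsistent missing-date rules: a drug with no start date but a known stop before the first dose is concomitant under one and prior under the other

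*SAP*

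**What the plan says.** SAP 5.8 opens with the definitions: "Prior used medications (discontinued before the start of study drug) and concomitant medications (on medication at the first dose of study drug or after". For a drug that has been stopped, the stop date relative to the first dose is therefore what counts.

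Two rules for incomplete dates follow.

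- **Unconditional rule**, in the same paragraph: "If the end-date and/or start-date are missing, the medication will be allocated to the concomitant medication". The and/or makes a missing start date enough on its own.
- **Conditional rule**, in the next paragraph. It applies when a date or time is missing or partly missing and "it cannot be determined whether it was taken prior to or concomitantly with treatment, it will be considered a concomitant medication".

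SAP 4.2 handles partial dates separately: "Partial dates will be reviewed and imputed (where possible) after the BDRM and before unblinding". Its default for an incomplete start date may move that date to the first dosing date, but with an exception: "unless the known end date lies before the first date of dosing, when imputing the incomplete start date". This covers a missing day, or a missing day and month. It gives no rule for a start date that is missing altogether.

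SAP 6.9 restates the stop-date definition relative to the first open-label dose, then adds: "Data conventions are as described in Section 5.8".

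**The concern.** A record with no start date and a stop date before the first dose is prior by definition and concomitant under the unconditional rule. The conditional rule would leave it prior, because the stop date shows when use ended. Nothing in SAP 5.8 says which rule takes precedence, so the output depends on which one the programmer codes.

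Such records are foreseeable. Protocol 15.4 limits medication history to 90 days before Screening, "with the exception of anti-dementia medications, where lifetime use (as far as possible) is to be recorded". A subject who once took an AChEI or memantine must have been off it for at least 60 days at the baseline assessments, so the stop has to be placed in time, while the start may lie years back.

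The main exposure is the concomitant-medication tabulations by treatment group in the ITT and ITTv5 populations. This is a monotherapy trial in which these drugs are disallowed. A table that shows them as concomitant when they had been stopped would misdescribe the study and would disagree with the separate AChEI/memantine listing in the same section.

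**Working it through.** The plan states no figure on this point and no arithmetic applies. The check is to take a record whose start date is fully missing and run it through the definition and both rules.

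| Stop date | Definition (SAP 5.8) | Unconditional rule | Conditional rule |
|---|---|---|---|
| (a) Known, before first dose | Prior | Concomitant | Not triggered, so prior |
| (b) Known, on or after first dose | Concomitant | Concomitant | Not triggered, so concomitant |
| (c) Missing | Cannot be placed | Concomitant | Concomitant |

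Only row (a) gives different answers.

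**Other date patterns.**

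- Partial start, known stop before first dose: SAP 4.2 imputes the start and does not move it past the known stop. On the ordinary reading that imputation comes before allocation, the start is no longer missing and the drug is prior. No conflict.
- Known start before first dose, fully missing stop: the unconditional rule gives concomitant. The conditional rule does too, because timing cannot be determined. No conflict.

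**Where row (a) can reach.**

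- *Concomitant-medication tables (SAP 5.8)*: directly, since they are built on the allocation.
- *Open-label tables (SAP 6.9)*: by the imported conventions. The equivalent record has no start date and a known stop before the first open-label dose.
- *Serotonergic subgroup of the adverse-event groupings (SAP 5.12.2)*: possibly. The subgroup is worded as "Use or no use of concomitant medications with serotonergic potential", but the line goes on to require use at some time during the study. It cites Section 5.8 for the drug list, not for the date convention. Carry-over happens only if the 5.8 flag is used in place of that condition.
- *Day 1 blood-pressure subset (SAP 5.12.4)*: possibly. It depends on concomitant SSRI, SNRI or MAOI use at Baseline, and the SAP does not say how that is derived.
- *Table of SSRI/SNRI, serotonergic and antipsychotic treatments (SAP 5.8)*: not shown. It counts treatments that were initiated.
- *Efficacy*: not shown. The MITT analyses drop assessments made after an AChEI or memantine was initiated, and those are identified before unblinding (SAP 5.9). Intercurrent event 3 of the primary estimand (SAP 5.9.1.1) also rests on initiation.

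**The case against.** The best defence is that the conditional rule is the operative one and the unconditional sentence is shorthand for it. SAP 4.2 supports that reading, since its exception for incomplete start dates lets a known pre-dose stop govern. On this view nothing is misclassified. It stands to this extent: a reader might infer that the SAP's settled rule counts stopped AChEI, memantine and serotonergic drugs as taken on study, and the documents do not support that. They contain two rules, and one of them gives the right answer. But the conditional rule does not say that it overrides the other, and SAP 4.2 does not reach a fully missing start.

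A second defence is that such records may be rare. Protocol 15.1 collects how long an AChEI or memantine was used and when it was stopped. SAP 5.8 plans a listing of start and stop dates and tabulates duration of use and time since stopping, so start dates are expected and the fact of stopping stays visible. That is fair, and it limits the harm without removing the inconsistency.

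A reader might also infer that the SSRI/SNRI and MAOI adverse-event subgroups are affected. SAP 5.12.2 describes these only as use or no use and does not refer to the 5.8 allocation, so this would be inference.

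**Conclusion.** The inconsistency is real but minor. It concerns only records with a fully missing start date and a known stop before the first dose (in SAP 6.9, before the first open-label dose). For these the unconditional rule contradicts both the section's own definition and the paragraph that follows it.

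The size cannot be computed. One could multiply an assumed share of prior AChEI/memantine users by an assumed share of records without a start date, but neither figure is in the documents, and the product would treat records as if they were subjects.

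The demonstrated effect is on descriptive medication tables, in both phases. An effect on the serotonergic adverse-event subgroup and the Day 1 blood-pressure subset is possible and depends on programming. It may be tempting to infer that AChEI/memantine exclusions in the efficacy analyses are contaminated. The documents do not support this, because those exclusions depend on initiation of treatment and not on the date default. The conclusion assumes that missing in the unconditional rule means fully missing after the SAP 4.2 imputation.

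**What to change.** Replace the unconditional sentence in SAP 5.8 with a rule to this effect: *a medication with a known stop date before the first dose is prior, whatever its start date; it is concomitant if the stop date falls on or after the first dose, or if its timing cannot be determined.* In SAP 6.9, state the same rule relative to the first open-label dose.

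The drafting cost is a sentence in each section. There is a small further cost. SAP 3.0 (7 June 2023) was issued after the data snapshot of 28 April 2022 and the partial unblinding for the double-blind analysis, so this should be recorded in SAP Section 10 as a post-unblinding change. The statistics vendor should check which rule was programmed and count the records with no start date and a pre-dose stop. If there are none, or they were already treated as prior, only the text changes. Otherwise the concomitant-medication tables need re-running, together with the serotonergic subgroup and Day 1 blood-pressure outputs if those used the same flag.
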